5.2 Safety analysis set

The analysis set consisting of all randomly allocated subjects excluding the following subjects is the safety analysis set.

- ✓ Subjects who have never received a dose of the study drug
- ✓ Subjects with no post-randomization safety data

5.3 Pharmacokinetics analysis set

Pharmacokinetics analysis set consists of all randomly allocated subjects excluding the following subjects:

- ✓ Subjects who have never received a dose of MT-6548 tablets
- ✓ Subjects with no post-randomization plasma drug concentration data

6. Patient Cohort

The patient cohort is defined as follows: Analyses will be performed for each patient cohort as needed.

- ✓ Correction cohort: A group of patients who have not received ESA formulations from 8 weeks prior to the first day of the screening period.
- ✓ Conversion cohort: A group of patients who have received ESA formulations from 8 weeks prior to the first day of the screening period.
- ✓ Conversion (Hb level ≥ 11.0) cohort: A subset of patients in the Conversion cohort whose mean Hb level during the last 2 screening sessions is ≥ 11.0 g/dL.
- ✓ Conversion (Hb level < 11.0) cohort: A subset of patients in the Conversion cohort whose mean Hb level during the last 2 screening sessions is < 11.0 g/dL.

7. Data Handling

The fixed data of the treatment period phase 1 should be handled as follows: The handling of data other than the following (excluding handling of data related to pharmacokinetic assessment) should be decided in the case review meeting and specified in the statistical analysis plan that will be fixed finally by the data fixation.

7.1 Handling of missing data

If test measurements are missing or if problems with samples etc. result in invalid measurements or reference values, these should be handled as missing values. Derived variables should also be treated as missing if even one test value or other data required for derivation is missing or not adopted.

7.2 Handling of data for tabulation at each evaluation time point

Data that meet the permitted range specified in the “Table 9.1-1 Permitted range of study visits” section of the protocol should be used for the tabulation at each evaluation time point and should not be imputed with those outside the permitted range.

If there are multiple data within the permitted range, then the one closer to the reference date should be adopted. If the deviations from the reference date are the same, data for the efficacy and safety evaluations should be adopted before and after the reference date, respectively.

7.3 Handling of efficacy endpoints if rescue therapy is performed

If rescue therapy is performed, data from the day after rescue therapy should not be used to assess efficacy.

7.4 Imputation of missing data

The mixed repeated-measures model (MMRM) used to analyze the primary efficacy endpoint should not use data imputing missing data, except for the first day of the treatment period.

If there are missing values at the first day of the treatment period, data from the day closest to the first day of the treatment period should be used as data for the first day of the treatment period.

Mean Hb values at Weeks 20 and 24 of the treatment period should be derived as data for analysis of covariance (ANCOVA), which is performed as a sensitivity analysis for the primary efficacy endpoint. Missing data are imputed with data from the evaluation time point immediately before the missing evaluation time point (excluding the first day of the treatment period) (LOCF method). When any one evaluation time points has missing values, the data at the evaluation time point closest to the missing evaluation time point is adopted, and when two evaluation time points have missing values, the data in the two different evaluation time points closest to and before the missing evaluation time points should be adopted to calculate the mean Hb value. However, Hb values at the same evaluation time point should not be used.

In addition, for clinical laboratory values, vital signs, and QOL indices among the efficacy endpoints, values imputed by the LOCF method at Week 24 of the treatment period should also be output. Data obtained by imputing missing values at Week 24 of the treatment period should be used as data at the end of the treatment period phase 1.

7.5 Handling of clinical laboratory test values less than the limit of quantification

If the measured values are reported to be not more than the limit of quantification, less than the limit of quantification, or impossible to calculate, the following handling procedures should be applied for tabulation, and missing values or zero values should not be used.

[Handling of quantification limit values]

(1) If the measurement is reported as less than the limit of quantification

The value obtained by adding the following processing to the limit of quantification value is used as an alternative value for tabulation.

- 1) After checking the number of significant figures of the applicable item, 1 should be subtracted from the significant figure of the lowest reported quantification limit value.
- 2) It should then be expanded by one digit to a smaller number and 9 is set.

Example) Report: less than 3 Effective number of the measuring facility: up to ones digit

→ Tabulation handling: 2.9

Report: less than 500 Effective number of the measuring facility: up to tens digit

→ Tabulation handling: 499

- (2) When the measured value is reported as not more than the limit of quantification or not less than the upper limit of quantification, the limit of quantitation itself should be used as a substitute value for tabulation.

Example) Not more than the limit of quantification

Report: 10 or less → Tabulation handling: 10 Not less than the limit of quantification

Report: ≥20 → Tabulation handling: 20

- (3) When the measured value used in the calculation is less than or not more than the quantification limit and the test result is reported as “Unable to be calculated” (Urine albumin/creatinine ratio, urinary protein/creatinine ratio), the measured value used in the calculation is added with the above processing as an alternative value, calculation is performed using the following calculation formula, and the calculation result is used for tabulation.

[Arithmetic expression]

- Urine albumin/creatinine ratio = $100 \times \text{Urine albumin}/\text{Urine creatinine}$
- Urine protein/creatinine ratio = $1000 \times \text{Urine protein assay (concentration)}/\text{Urine creatinine}$

7.6 Handling of PK-related data

Blood sampling days for plasma drug concentration measurements should be set as described in “Table 9.1-1 Permitted ranges for study visits” in the study protocol. When it is necessary to examine the handling of data, such as when the day of blood sampling is outside the permitted range, when there is a deviation from the study protocol, or when the plasma collection procedure is not observed, the sponsor should decide whether to collect and analyze drug concentration data after the case review meeting.

8. Statistical Method

Data for up to Week 24 of the treatment period phase 1 will be fixed when all subjects have completed treatment period Phase 1. Statistical analysis will be conducted for the treatment period phase 1 fixed data.

8.1 Basic Matters

8.1.1 Level of significance and confidence coefficient

When implementing tests, level of significance should be set at 2-sided 5%. Confidence interval will be 2-sided with a confidence coefficient of 95%.

8.1.2 Descriptive statistics to calculate

Types of continuous variables to be calculated for each descriptive statistics item are provided below.

Number of subjects, mean, standard deviation (SD), median, minimum, maximum, and 2-sided 95% CI of the mean

8.1.3 Number of digits displayed

The number of digits to be displayed in the analysis results will be as follows.

Numeric content	Number of display digits
p value	3 decimal places, however, when it is less than 0.001, it will be described as “< 0.001”.
Proportion (percentage)	Integer part + 1 decimal places
Rate of change	Integer part + 1 decimal places
Descriptive statistics (minimum and maximum)	Same as the number of digits as original variable
Descriptive statistics (mean, SD, median)	Number of digits of the original variable + 1 digit
Hb increase rate	Integer part + 4 decimal places
QOL (EQ-5D-5L) index value	Integer part + 3 decimal places

Hepcidin will be measured in units of pg/mL; however, the unit used for tabulation should be ng/mL, and the number of displayed digits should be two decimal places.

8.2 Breakdown of subjects

8.2.1 Disposition

For subjects enrolled in the treatment period, the breakdown of each analysis set in each treatment group should be provided. The breakdown of patient cohort will also be provided.

Item: Number of subjects enrolled in treatment period, FAS subject number and its proportion, FAS exclusion subject number and its proportion, PPS subject number and its proportion, PPS exclusion subject number and its proportion, safety analysis set subject number and its proportion, safety analysis set exclusion subject number and its proportion, drug concentration analysis sets and its proportion, drug concentration analysis sets exclusion subject number and its proportion

8.2.2 Subjects who discontinued or interrupted their treatment

For subjects enrolled in the treatment period, the number and proportion of discontinued subjects should be calculated in each treatment group and by reasons for discontinuation.

Item: Number and proportion of discontinued subjects by treatment group and the number and proportion of reasons for discontinuation for subjects enrolled in treatment period,

For subjects enrolled in the treatment period, the number of cases of drug interruptions should be tabulated by treatment group and the number and proportion of reasons for interruption should be tabulated. The denominator of the proportion should be the sum of the number of interruption cases. If there are multiple reasons for a single interruption, they should be counted for each reason and stated as the number of interruption cases.

Item: Number and proportion of cases of drug interruptions in subjects enrolled in the treatment period and the number and proportion of reasons for drug interruptions

8.3 Demographic and other baseline characteristics

For each analysis sets (except PK analysis set), the major demographic and other baseline characteristics should be summarized by treatment group. Frequency and proportion will be provided for discrete variables and descriptive statistics for continuous variables (no calculation of 95% CI of the mean). If the PPS or safety analysis set is the

16.1.9 Documentation on Statistical Methodology

Confidential

same as the FAS, the results for the analysis sets will not be presented. The data should also be summarized in the FAS by patient cohort.

Table 8.3 Characteristics of demographic and other baseline characteristics

Category	Item	Type of variables
Subject background	Sex (male, female)	Dichotomous
	Age (years) as of informed consent	Continuous
	2 categories: <65, ≥65	Dichotomous
	2 categories: <75, ≥75	Dichotomous
	Duration of nephrogenic anemia (years)	Continuous
	3 categories: <1, 1 to <5, ≥5	Ordinal
	Height (cm)	Continuous
	Body weight (kg)	Continuous
	BMI (kg/m ²)	Continuous
	2 categories: <25, ≥25	Dichotomous
Race		
	3 categories: not Hispanic or Latino, Hispanic or Latino, Unknown	Polytomous
Ethnicity		
	3 categories: Asian (Japanese), Asian (other), other	Polytomous
Smoking status	Presence or absence of smoking status 3 categories: never smoked, ex-smoker, current smoker	Polytomous
Underlying cause of CKD	Underlying cause 8 categories: diabetes mellitus, hypertension, autoimmune/glomerulonephritis/vasculitis, interstitial nephritis/pyelonephritis, cystic/hereditary/congenital disease, neoplasm/tumor, unknown, other	Polytomous
Complication	Presence or absence of complications on the first day of the treatment period	Dichotomous
	Presence or absence of hypertension	Dichotomous
	Presence or absence of diabetes mellitus	Dichotomous
	Presence or absence of dyslipidemia	Dichotomous

Previous ESA formulation (Conversion cohort only)	Types of previous ESA formulation 4 categories: epoetin alfa or epoetin beta, darbepoetin alfa, epoetin beta pegol, other.	Polytomous
	Frequency of administration by type of previous ESA formulation 7 categories: once a week, twice a week, three times per week, every 2 weeks, every 3 weeks, every 4 weeks, other	Polytomous
	Weekly dose (IU) of epoetin alfa or epoetin beta	Continuous
	Weekly dose of darbepoetin alfa (µg)	Continuous
	Weekly dose of epoetin beta pegol (µg)	Continuous
Evaluation data	Hb value (g/dL) on the first day of the treatment period 3 categories: <9, 9 to <11, ≥11	Continuous
	eGFR on the first day of the treatment period (mL/min/1.73 m ²) 4 categories: <15, 15 to <30, 30 to <60, ≥60	Continuous
	Liver function test (U/L) on the first day of the treatment period 3 categories: AST and ALT are both not more than the upper limit of normal, either is more than the upper limit of normal and both are not more than 2 times the upper limit of normal, either is more than 2 times the upper limit of normal	Trichotomous
	CRP (mg/dL) on the first day of the treatment period	Continuous
	Serum ferritin (ng/mL) on the first day of the treatment period 2 categories: <100, ≥100	Continuous
	TSAT (%) on the first day of the treatment period 2 categories: <20, ≥20	Dichotomous
	With or without iron supplements on the first day of the treatment period 2 categories: oral, intravenous	Continuous
	With or without iron-containing phosphate binders on the first day of the treatment period	Dichotomous
		Dichotomous

8.4 Study drug administration/treatment period and study drug administration/compliance status

For FAS and safety analysis set, the descriptive statistics of the study drug administration/compliance rate (no calculation of 95% CI of the mean) will be calculated by treatment group to provide the number and rate of subjects with study drug compliance rate of $\geq 80\%$ and $< 80\%$. Analysis will be performed by patient cohort in the FAS.

For FAS and safety analysis set, the descriptive statistics of the study drug administration/treatment period (no calculation of 95% CI of the mean) will be calculated by treatment group. Analysis will be performed by patient cohort in the FAS.

For FAS and safety analysis set, the descriptive statistics of the cumulative dosage of study drug (no calculation of 95% CI of the mean) will be calculated by treatment group.

8.5 Efficacy analysis

As a general rule, efficacy analysis will be performed on the FAS. When necessary, descriptive statistics for continuous variables should be calculated and frequency and proportion will be calculated for discrete variables. Unless otherwise specified, a similar analysis will be conducted for patient cohort. No data from the day after the rescue therapy implementation date should be included in the efficacy analysis.

- The defect mechanism of the missing not at random is be assumed, and the tipping point analysis will be performed after 1000 times of multiple imputation using the fully conditional specification regression method. For the data with multiple imputation, a similar analysis should be performed using the same MMRM model as that used for the primary efficacy endpoint, mean Hb at Week 20 and Week 24 of the treatment period. When non-inferiority is not established in the results of the tipping point analysis, LSMean, its standard errors, and 2-sided 95% CI of the mean Hb of Week 20 and Week 24 of the treatment period should be provided by

16.1.9 Documentation on Statistical Methodology

Confidential

treatment group. Furthermore, point estimate, its standard errors, and 2-sided 95% CI should be provided for LSMean of between-group differences (MT-6548 – darbepoetin).

- **Sample SAS code**

- Using analysis of covariance (ANCOVA) with the Hb value on the first day of the treatment period as a covariate, the LSMean, its standard errors, and 2-sided 95% of mean Hb at Week 20 and Week 24 should be provided by treatment group. Furthermore, point estimate, its standard errors, and 2-sided 95% CI should be provided for the between-group differences (MT-6548 – darbepoetin) of LSMean. If data from Week 20 and Week 24 of the treatment period are missing, data should be imputed by the methods described in “7.4 Imputation of missing values”.

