13.3.2 Efficacy

(1) Analysis methods for primary endpoint

For the primary endpoint of mean Hb at treatment period Weeks 20 and 24, mean Hb at each timepoint will be modeled using MMRM with the following model, mean Hb at treatment period Weeks 20 and 24 will be calculated for each group, and point estimates and their two-sided 95% CI will be calculated for differences in mean values between the MT-6548 group and the darbepoetin group. Non-inferiority of MT-6548 to darbepoetin alfa (recombinant) will have been established if the lower limit of the 95% CI is ≥ -0.75 g/dL.

[MMRM model]

- Covariates: Baseline values
- Fixed effects: Treatment group, evaluation period, patient cohort (correction or conversion cohort), interactions of evaluation period \times treatment group, interactions of evaluation period \times patient cohort (correction or conversion cohort)
- Random effects: Subjects

The non-inferiority of the MT-6548 group with the darbepoetin group will be assessed after the mean of mean Hb values at treatment period Weeks 20 and 24 and its 95% CI is confirmed to fall within the target range of Hb values (11.0–13.0 g/dL).

Sensitivity analysis will be performed using the following analysis methods.

- Tipping point analysis
- ANCOVA using data with missing values imputed by LOCF and baseline values as covariates

(2) Analysis methods for secondary endpoints

1) Mean Hb at treatment period Weeks 48 and 52

Treatment groups will be compared using the same analysis methods (MMRM) used for the primary endpoint. Point estimates and their standard errors and 95% CI will be calculated for differences in mean values between the MT-6548 group and the darbepoetin group.

2) Hb at each treatment period timepoint

Descriptive statistics will be calculated for Hb levels at each treatment period timepoint, and analysis performed taking into account changes over time using MMRM.

- 3) Ratios of subjects with mean Hb within the target range (11.0–13.0 g/dL), <11.0 g/dL, and ≥ 13.0 g/dL at each timepoint in treatment period

Numbers and ratios of subjects with mean Hb at each treatment period timepoint within the target range (11.0–13.0 g/dL), <11.0 g/dL, and ≥ 13.0 g/dL will be shown.
- 4) Correction cohort only: Days from initiation of treatment period required to reach target Hb range (11.0–13.0 g/dL)

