2.5 Rationale for sample size

A total of 300 subjects (150 each for the MT-6548 and darbepoetin groups) should be enrolled in the treatment period. The target sample size for each cohort is shown below.

- ✓ Correction cohort: 100 subjects
- ✓ Conversion cohort: 200 subjects

However, the maximum number of subjects with mean screening period Hb values (mean of 2 most recent central testing facility results) of <11.0 g/dL and ≥ 11.0 g/dL in the screening period in the Conversion cohort should be 120.

[Rationale]

For the primary efficacy endpoint of mean Hb values at treatment period Weeks 20 and 24, the mean Hb value in the darbepoetin group is assumed to be 12.0 g/dL, the difference between the MT-6548 and darbepoetin groups is assumed to be 0 g/dL, and the standard deviation for both is assumed to be 1.78 g/dL. The non-inferiority margin is set at -0.75 g/dL. Calculation of statistical power from these assumptions shows that a sample size of 150 subjects in each group would ensure greater than 95% probability that the mean of mean Hb values in the MT-6548 group and their 95% CI would fall within the target Hb range (≥ 11.0 to < 13.0 g/dL) and non-inferiority could be established.

In addition, the target sample size was set for each of the Correction cohort, Conversion cohort, Conversion (Hb value ≥ 11.0 g/dL) cohort, and Conversion (Hb value < 11.0) cohort so that appropriate evaluation could be made for each cohort.

The assumed standard deviation was set at 1.78 g/dL based on the upper limit of the 80% confidence interval of the standard deviation in the MT-6548 300 mg group at Week 6 in study CI-0021.

3. Endpoints

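### The LOCF ANCOVA sensitivity analysis, as described, leaves out patient cohort, a randomisation factor that the primary MMRM adjusts for; adding it is a free improvement

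*SAP*

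**What the plan says.** Phase 1 SAP 2.3 and Protocol 5.3.1 stratify randomisation by cohort and, within cohort, by mean screening Hb. The primary MMRM (Phase 1 SAP 8.5.1, Protocol 13.3.2) has baseline Hb as covariate and, among its fixed effects, treatment, time point, cohort, time by treatment and time by cohort. The screening-Hb stratum is not in it.

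Two sensitivity analyses are planned. The tipping-point analysis reuses the primary MMRM after multiple imputation, so cohort stays in. The other is an ANCOVA on LOCF data:

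- Protocol 13.3.2: "ANCOVA using data with missing values imputed by LOCF and baseline values as covariates".
- Phase 1 SAP 8.5.1: "Using analysis of covariance (ANCOVA) with the Hb value on the first day of the treatment period as a covariate".
- Phase 1 SAP 8.5.4.1 repeats this, again naming only the first-day value.

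Cohort appears in none of the three. Phase 1 SAP 7.4 gives the intended contrast: LOCF for the ANCOVA, no post-baseline imputation for the MMRM.

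**The concern.** An analyst who follows the text would fit treatment and baseline Hb only. That has two consequences.

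First, when randomisation is balanced within a prognostic factor and the analysis ignores it, the variation between the cohorts stays in the residual. The treatment estimate is still well balanced, but its reported standard error is too large.

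Second, a sensitivity analysis is easiest to read when it changes only what it is meant to test. This one changes the missing-data handling, replaces a repeated-measures model by a single-endpoint model, and also drops a model term. The third change serves no stated purpose.

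A cohort effect beyond baseline Hb is plausible. The cohorts differ in prior ESA exposure, entry Hb range and darbepoetin starting rules, and the sponsor both stratified on cohort and modelled it by time. The documents give no figure for its size.

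**Working it through.** **The plan's own figure.** Inputs from Phase 1 SAP 2.5: "A total of 300 subjects (150 each for the MT-6548 and darbepoetin groups) should be enrolled in the treatment period"; "The non-inferiority margin is set at -0.75 g/dL"; "the difference between the MT-6548 and darbepoetin groups is assumed to be 0 g/dL"; "the standard deviation for both is assumed to be 1.78 g/dL". Non-inferiority is judged from a two-sided 95% CI.

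SE = 1.78 × √(2/150) = 0.2055. Power = Φ(0.75/0.2055 − 1.96) = Φ(1.69) = 95.4%. The added condition that the MT-6548 mean and its CI lie within 11.0–13.0 g/dL is met almost always, so the joint probability is also 95.4%. The SAP's statement that "a sample size of 150 subjects in each group would ensure greater than 95% probability" is reproduced.

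**Effect of leaving cohort out.** Let d be the cohort difference in Week 20/24 Hb at equal baseline Hb, and s the residual SD within cohort. The planned cohort sizes are 100 and 200, so cohort has variance (1/3)(2/3) = 0.222. If cohort were unrelated to baseline Hb, the ratio of standard errors (without cohort to with cohort) would be √(1 + 0.222 d²/s²). For d from 0.25 to 1.0 that gives an excess of 0.2–3.4% at s = 1.78 and 0.7–10.6% at s = 1.0.

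Those figures are too high, because baseline Hb already carries part of the cohort information. Take baseline Hb as uniform over the eligibility ranges (an assumption): 8.0–11.0 for correction and 9.0–12.5 for conversion.

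- The means are 9.5 and 10.75, so the between-cohort variance is 0.222 × 1.25² = 0.347.
- The within-cohort variance is (1/3)(3²/12) + (2/3)(3.5²/12) = 0.931.
- Baseline Hb explains 0.347/(0.347 + 0.931) = 27% of cohort.
- The cohort variance left over is 0.222 × 0.728 = 0.162.

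The ratio becomes √(1 + 0.162 d²/s²). A simulation of 3,000 stratified trials per scenario (same baseline ranges, baseline slope 0.5, no missing data) fitted the ANCOVA with and without cohort:

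| s | d | Formula | Simulated SE, without / with cohort | Excess |
|---|---|---|---|---|
| 1.78 | 0 | 1.000 | 0.2054 / 0.2054 | none |
| 1.78 | 0.5 | 1.006 | 0.2067 / 0.2054 | 0.6% |
| 1.78 | 1.0 | 1.025 | 0.2107 / 0.2054 | 2.6% |
| 1.0 | 0.5 | 1.020 | 0.1178 / 0.1154 | 2.0% |
| 1.0 | 1.0 | 1.078 | 0.1245 / 0.1154 | 7.9% |

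**What this does to the result.**

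- The actual spread of the estimates hardly changes: at s = 1.78 and d = 1.0 it is 0.2072 without cohort and 0.2070 with it.
- For d of 0.5 to 1.0, the two point estimates differ on average by 0.005–0.011 g/dL, against a margin of 0.75.
- Without cohort, coverage of the 95% CI is 95.3–95.6% at s = 1.78 for these gaps, and 96.7% at s = 1.0 with d = 1.0.
- At s = 1.78, the chance of showing non-inferiority falls from 95.5% to 95.2% (d = 0.5) or 94.7% (d = 1.0).

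**The case against.** The strongest reply is that the omission is inferred from silence. The plan lists covariates separately from fixed effects, and the ANCOVA sentences name only the covariate. Phase 1 SAP 8.5.4.1 describes the MMRM in the same short way, yet that model does contain cohort. The sample SAS code is not visible in the public text, so a cohort term cannot be ruled out. This stands as a caution. But the MMRM has a full list of terms elsewhere and the ANCOVA has none, so the written plan leads to a model without cohort.

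It is also fair to say that both cohorts are titrated to the same 11.0–13.0 g/dL target, which argues against a large gap at Weeks 20 and 24. Hence d = 0 belongs in the range, and there nothing is lost.

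Two stronger readings are tempting and not supported:

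- **That the ANCOVA's CI is wider than the primary CI.** The documents do not determine this. LOCF keeps the subjects it can impute, while the MMRM gains no observations. If 5–20% of values were missing (assumed), a completers-only analysis would raise the SE by 1/√(1 − m) − 1 = 2.6–11.8%. That is an upper bound on the MMRM's loss, and it could outweigh the effect of cohort.
- **That a discrepancy with the MMRM could not be attributed to missing data because cohort was dropped.** Under stratified randomisation the dropped term moves the estimate by about 0.01 g/dL or less on average, so a material discrepancy would have to come mainly from elsewhere. Nor would adding cohort isolate the missing-data effect, since the single-endpoint form remains. The tipping-point analysis is the one that holds the model fixed.

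**Conclusion.** The point holds in a limited form and is a free improvement. As described, the LOCF ANCOVA omits a randomisation factor that the primary model includes. If cohort is prognostic beyond baseline Hb, its reported SE is too large relative to the same ANCOVA with cohort, by the 0.6–2.6% shown above at the planning SD and by up to about 8% at SD 1.0. At SD 1.78 and a 1.0 g/dL gap, the 95% CI half-width is 1.968 × 0.2107 = 0.415 instead of 1.968 × 0.2054 = 0.404 g/dL, a difference of about 0.01.

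These sizes rest on assumed gaps, an assumed lower SD and assumed uniform baseline Hb, none of which the documents give. The direction is conservative: it makes non-inferiority slightly harder to show and does not favour MT-6548. The primary conclusion does not depend on this analysis.

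**What to change.** In Phase 1 SAP 8.5.1 and 8.5.4.1, write out the ANCOVA terms as treatment, baseline Hb and patient cohort, or confirm that the SAS code already includes cohort. The cost is one CLASS variable with one degree of freedom, using data already collected.

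Do not add the screening-Hb stratum. The primary MMRM does not contain it, so adding it would replace one mismatch with another, and it is close to the baseline Hb already in the model.

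If the Phase 1 data are already locked, report the ANCOVA with cohort as an added analysis, with the reason stated and the result kept distinct from the planned one, as Protocol 13.4 provides.
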